PHASE AND TYPE OF RESEARCH	Phase 1	
	Phase 2	
	Phase 3	
	Phase 4	
	Observational drug study	
	Medical device clinical research	

	Performance evaluation studies conducted with in vitro medical diagnostic devices	
	Non-drug clinical research	
Please specify if other:		

Research hypothesis:

$\mu \neq 0$ hypothesis: During extraction of mandibular impacted wisdom teeth, the trigeminocardiac reflex does not occur with stimulation of the peripheral branches of the trigeminal nerve.

$\mu = 0$ hypothesis: During extraction of mandibular impacted wisdom teeth, a trigeminocardiac reflex occurs by stimulation of the peripheral branches of the trigeminal nerve.

Introduction-Purpose Section

The trigeminocardiac reflex (TCR) has entered the scientific literature as an oculocardiac reflex with strabismus surgeries (1). In cases where the V1 branch of the trigeminal nerve forms the afferent pathway of the V1 branch of the trigeminal nerve, a clinical phenomenon with vagal stimulation findings has been encountered. Since the publication of TCR in ophthalmological surgery in 1908, it has become a well-known clinical picture for ophthalmologists and anesthetists (2). The anesthetist's mastery and experience in this picture, which is met by manipulation of the ocular muscles, is of great importance. Recognition that the picture is a brainstem reflex involving the vagal pathway is critical in mastering the clinical situation. In the literature, it has been reported that V2 and V3 branches of the trigeminal nerve can also produce the reflex picture and the reflex can be seen under local anesthesia. (3,4). Reflex is diagnosed under local anesthesia as well as under general anesthesia with hemodynamic data (blood pressure, heart rate) that can be monitored non-invasively.

TCR is a physiological, life-threatening response with sudden onset of severe bradycardia, hypotension and asystole with parasympathetic activation of the heart due to stimulation of the vagal nerve as a result of stimulation of any of the three branches of the trigeminal nerve. (1). It is defined as a decrease in heart rate and mean arterial blood pressure by more than 20% from baseline or a heart rate of less than 60 beats per minute due to intraoperative traction or manipulation of the trigeminal nerve. The afferent branch of the trigeminocardiac reflex arc is formed by the sensory nerve endings of the fifth cranial nerve. Neuronal signals are sent to the trigeminal sensory nucleus via the Gasserian ganglion. The sensory nucleus of the afferent reflex branch of the trigeminal nerve connects to the efferent pathway via short internuncial fibres in the reticular formation with the more distant motor nucleus of the vagus nerve. Cardioinhibitory efferent fibres originate from the motor nucleus of the vagus nerve. It transmits vagus-mediated negative chronotropic and inotropic responses to the heart and terminates in the myocardium (5).

In the maxillofacial surgery literature, there are case reports reporting the development of trigeminocardiac reflex in orthognathic surgery, dental implant surgery and maxillofacial trauma surgery and prevalence studies for major surgeries (6,7,8). Haemodynamic changes and neurological-based emergencies (e.g. vasovagal syncope) are quite common in routine oral surgical procedures performed under local anaesthesia (9).

In addition, in a study, it was noted that a significant decrease in heart rate and blood pressure occurred during extraction of posterior mandibular teeth and this may be related to the trigeminocardiac reflex (10). Extraction of impacted wisdom teeth is one of the commonly performed procedures in the field of oral and maxillofacial surgery. To the best of our knowledge, there is no study in the literature evaluating the development of TCR during mandibular impacted wisdom tooth extraction.

Our aim was to investigate the trigeminocardiac reflex during oral surgical procedures routinely performed under local anaesthesia. Our reasons for choosing mandibular impacted wisdom tooth surgery among oral surgeries for this purpose are; the proximity of the inferior alveolar nerve, which is the largest terminal branch of the V3 branch of the trigeminal nerve, to the tooth roots and the frequent observation of traction on the nerve, the fact that there may be differences in the depth of effect between anaesthetic techniques due to the variation of the mandibular nerve, and our clinical experience. There are no studies in the literature evaluating the development of trigeminocardiac reflex during surgical treatment of mandibular wisdom teeth.

Materials and Methods Section:

The study will be conducted on patients referred to KSBÜ Faculty of Dentistry, Department of Oral, Dental and Maxillofacial Surgery from Oral, Dental and Maxillofacial Radiology, who have an indication for extraction of impacted mandibular wisdom teeth under local anesthesia, who will undergo extraction of impacted wisdom teeth for the first time, who agree to have the surgical extraction of these teeth performed at KSBÜ Faculty of Dentistry, Department of Oral, Dental and Maxillofacial Surgery and who agree to participate in the study.

If there is a clinical necessity, cone beam computed tomography will be taken to evaluate the relationship of impacted wisdom teeth with the nervus alveolaris inferior and to evaluate their localization in the mandible in three dimensions. In patients who do not need tomography, the evaluation will be performed with Orthopantomogram film. The distance of the relevant wisdom tooth roots from the inferior alveolar nerve will be recorded.

During the procedure, Gow-Gates and nervus alveolaris inferior anesthesia techniques, which are the two most commonly used local anesthesia techniques in oral, dental and maxillofacial surgery practice, will be applied for the extraction of mandibular impacted teeth.

Patients will be divided into 2 groups according to the proximity of the wisdom tooth roots to the inferior alveolar nerve (1 mm and closer to the nerve / more than 1 mm away from the nerve) and 2 groups according to the anesthesia technique to be applied (Gow-Gates Block - Inferior alveolar block). Total research arm is 4.

In the research arms we have established, the follow-up of TCR that may occur during the procedure will be provided by monitoring the patients (Contec Medical Systems, Hebei, China.) Heart rate, systolic and diastolic blood pressure, oxygen saturation will be recorded during the procedure. The records will be taken in 4 stages: before starting the surgical procedure, during the application of local anaesthesia, during the incision, during the elevation of the crown and root. Sudden changes that occur during the procedure will be recorded together with the process in which they occur.

(e.g. during local anesthesia)

Initial heart rate: 80 beats/min

End of procedure heart rate: 78 beats/min

Sudden presence of bradycardia or tachycardia during the procedure;

Sudden change in heart rate: 80>58 or 80>98)

During extraction of impacted wisdom teeth, a 20% decrease in heart rate and a decrease in heart rate below 60 will be considered as the development of TCR in parallel with the literature. The prevalence of TKR will be evaluated in 4 separate groups according to whether Gow-Gates anaesthesia or nervus alveolaris inferior anaesthesia is applied and whether the wisdom teeth are closer than 1 mm and 1 mm or further than 1 mm from the nervus alveolaris inferior.

During mandibular impacted wisdom tooth extraction, patients will be monitored and the following parameters will be evaluated:

1. Systolic blood pressure
2. Diastolic blood pressure
3. Oxygen saturation
4. Heart rate

The anxiety level of the patients will be assessed with the Amsterdam Preoperative Anxiety and Information Score Scale (APAIS) and State-Trait Anxiety Inventory (STAI-S) in order to differentiate TKR from common neurological emergencies (e.g. vasovagal syncope) due to dental phobia. State Anxiety Scale was developed in 1970 and its Turkish form was adapted in 1983 and validity and reliability study was conducted. APAIS was translated into Turkish for the first time in our country in 2007 and it was found that APAIS and STAI-S were correlated with each other in the studies conducted(11).

STAI-S (The State-Trait Anxiety Inventory)

Amsterdam Preoperative Anxiety and Information Scale (APAIS)

	Not all 1	2	3	4	Very much 5
I am worried about anesthetics					
The anesthetics is on my mind continually					
. I would like to know as much as possible about the anesthetic					
I am worried about the procedure.					
The procedure is on my mind continually.					
I would like to know as much as possible about the procedure					

		No t at all	A little	So me wha t	Very Much So
1.	I feel calm	(1)	(2)	(3)	(4)
2.	I feel secure	(1)	(2)	(3)	(4)
3.	I feel tense	(1)	(2)	(3)	(4)
4.	I feel strained	(1)	(2)	(3)	(4)
5.	I feel at ease	(1)	(2)	(3)	(4)
6.	I feel upset	(1)	(2)	(3)	(4)
7.	I am presently worrying over possible misfortunes	(1)	(2)	(3)	(4)
8.	. I feel satisfied	(1)	(2)	(3)	(4)
9.	I feel frightened	(1)	(2)	(3)	(4)
10.	I feel uncomfortable	(1)	(2)	(3)	(4)
11.	I feel self confident	(1)	(2)	(3)	(4)
12.	I feel nervous	(1)	(2)	(3)	(4)
13.	I feel jittery	(1)	(2)	(3)	(4)
14.	I feel indecisive	(1)	(2)	(3)	(4)
15.	I am relaxed	(1)	(2)	(3)	(4)
16.	I feel content.	(1)	(2)	(3)	(4)
17.	I am worried	(1)	(2)	(3)	(4)
18.	I feel confused	(1)	(2)	(3)	(4)
19.	I feel steady	(1)	(2)	(3)	(4)
20.	I feel pleasant.	(1)	(2)	(3)	(4)

Inclusion criteria:

Patients aged 18-30 years

Patients without any systemic problems

Patients with an indication for extraction of mandibular wisdom teeth

Patients have no previous experience of impacted tooth extraction

Exclusion criteria:

Female patients who are pregnant or breastfeeding
Patients with systemic problems
Patients with mental or neurological disorders
Patients taking antidepressants
Patients with cardiovascular problems

Sample Selection and the statistical method to be used:

Since the study population was not known, the power and sample level of the study were calculated with reference to the study of Bohluli (2011). Bohluli (2011) studied with n=20 patients in his study. According to the study of Bohluli (2011), it is seen that n=20 patients planned to be included in the study planned the study with 90% power (in studies, values of 0.70 and above are considered valid and 0.80 is considered to be quite sufficient). In the study, it was determined that the effect size level was 0.42. The study is planned to be conducted on a total of 40 patients. The groups were determined equally as Group 1 (IAS / less than 1 mm distance) n=10, Group 2 (IAS / more than 1 mm distance) n=10, Group 3 (IAS / less than 1 mm distance) n=10 and Group 4 (IAS / more than 1 mm distance) n=10.

Regarding the analysis of the data; descriptive statistics will be presented with mean-d.deviation, median-IQR, frequency and percentage values. In order to examine whether the measurements in the study are different according to the characteristics of the study groups, independent Mann Wihtney U test and Kruskall Wallis test analyses are considered. Paired Wilcoxon test and Friedman test analysis can be applied in the evaluations of repeated measurements. In determining the times that are significant as a result of Friedman test, it is considered to be determined by All-pairwise method. Spearman correlation analysis will be applied to examine the relationships between the measurement values of the groups. Chi-square analysis will be performed for the proportional evaluations of the groups. In the study, p values less than 0.05 are considered significant. The analyses will be analysed with SPSS 25.0. Power level and effect size calculations calculated in the study were determined with G*PowerVersion 3.1.7.

List of References

2. Aschner, B. (1908). Ueber einen Bisher noch nicht Beschriebenen Reflex vom Auge auf Kreislauf und Atmung: Verschwinden des Radialispulses bei Druck auf das. *Review of Oculocardiac Reflex When Facial Surgery*.

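### The TCR rule asks for a larger percentage fall the faster the heart rate starts, so TCR prevalence can differ between arms through starting rate alone

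*Protocol*

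**What the plan says.** The outcome rule is that "a 20% decrease in heart rate and a decrease in heart rate below 60 will be considered as the development of TCR". It stands in the Materials and Methods Section and is repeated in the application form under Scope of the research and under Evaluation of results (Outcome/Endpoint). The same places say what it is for: "The prevalence of TKR will be evaluated in 4 separate groups", formed by block technique and by root distance from the nerve.

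The worked example in the Materials and Methods Section has "Initial heart rate: 80 beats/min" and records "Sudden change in heart rate: 80>58 or 80>98".

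The definition in the Introduction-Purpose Section, repeated under Purpose of the research, is different. It requires heart rate and mean arterial pressure to fall "by more than 20% from baseline or a heart rate of less than 60 beats per minute".

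The statistical section says "Chi-square analysis will be performed for the proportional evaluations of the groups" and that "p values less than 0.05 are considered significant". It names no term for starting heart rate in that comparison. "The study is planned to be conducted on a total of 40 patients", 10 in each group. The design field describes a cohort, and no random allocation is stated. The entry criteria do not limit starting heart rate.

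**The concern.** A fixed floor of 60 beats/min, joined by 'and' to a relative fall, turns one outcome into different outcomes for different patients. A slow starter needs a 20% fall. A fast starter needs whatever fall reaches 60, which may be a third or more. The same relative response is then scored as a TCR in one patient and not in another.

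Two things are at stake. First, the headline prevalence leaves out some falls of 20% or more in patients who start fast. Second, a difference between blocks, or between near and far teeth, could reflect starting rate and not the reflex. Nothing in the stated design equalises starting rates: no randomisation is described and proximity is anatomical. The protocol also plans to relate haemodynamic change to anxiety. If anxiety raises the starting rate (an assumption), the rule makes anxious patients less likely to be scored, which bears on that analysis too.

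**Working it through.** **Inputs from the protocol.** Rule: fall of 20% and rate below 60. Example start: 80. Four groups of 10. Chi-square at 0.05. There is no stated figure to reproduce, because the protocol gives no heart-rate distribution and no expected TCR rate.

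**Step 1: the fall the rule requires.** Let B be the starting rate. Both limbs hold only if the later rate is at most 0.8 × B and also below 60. The required fall is therefore max(20%, 1 − 60/B). The limbs cross at B = 60/0.8 = 75.

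| Start B | 1 − 60/B | Fall needed |
|---|---|---|
| 70 | 14.3% | 20% |
| 75 | 20.0% | just over 20% |
| 80 | 25.0% | just over 25% |
| 85 | 29.4% | just over 29.4% |
| 90 | 33.3% | just over 33.3% |
| 100 | 40.0% | just over 40% |

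From 75 upward the values are lower bounds, since the rate must be strictly below 60. Above 75 the 20% limb never decides anything.

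**Step 2: single patients.** 70 to 56 is 14/70 = 20% and is scored. 80 to 61 is 19/80 = 23.8% and is not. 100 to 62 is 38/100 = 38% and is not. The protocol's 80 to 58 is 22/80 = 27.5%. It meets both limbs, so it does not settle 'and' against 'or'.

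**Step 3: the 'or' definition, heart-rate limbs only.** The fall needed becomes min(20%, 1 − 60/B): 20% from 75 upward, but 14.3% at 70, 7.7% at 65 and 3.2% at 62. This also depends on the start. Under both rules a slower start never makes scoring harder, and over part of the range makes it easier. (The full definition also asks for a fall in mean arterial pressure with the 20% limb.)

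**Step 4: possible size, on assumed inputs.** All heart-rate figures here are assumptions. Two groups of 20 (two cells pooled on one factor) have the same normal distribution of relative falls, unrelated to start. Starts are normal with SD 11 and means 78 v 88. Pearson chi-square at 0.05, 40,000 simulated trials per row:

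| Mean fall | SD of fall | TCR rates | False positives |
|---|---|---|---|
| 10% | 8% | 6% v 2% | under 2% |
| 10% | 10% | 9% v 4% | 5% |
| 15% | 10% | 19% v 9% | 13% |
| 20% | 10% | 33% v 18% | 19% |
| 25% | 10% | 50% v 30% | 23% |
| 25% | 8% | 50% v 28% | 29% |

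With a gap of 5 beats (78 v 83) at mean fall 20%, SD 10%, the rates are 33% v 26% and rejection is about 8.5%. With four groups of 10 (78, 78, 88, 88) and SD of fall 10%, rejection is about 3%, 7% and 11% at mean falls of 10%, 15% and 20%. Scored on relative fall alone, both arms agree and rejection stays at about 4–5.5%. With equal starts of 78 and mean fall 20%, SD 10%, the below-60 limb reduces the count from 50% to 33%.

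**Step 5: chance imbalance.** With equal mean starts, rejection under the two-limb rule is at or near 5% or lower. With SD 11 and 20 v 20, the standard error of the difference in mean starts is 11 × √(2/20) = 3.5 beats. A 10-beat gap is 10/3.48 = 2.87 standard errors, p about 0.004.

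**The case against.** The strongest reply is that the consequence is hypothetical. The documents give no heart rates, and nothing in them suggests that root-to-nerve distance or choice of block goes with pre-operative heart rate. Chance imbalance is already covered by the test's own error rate. If TCR is uncommon, even a 10-beat gap produces no excess of false positives. All of this stands. A reader might infer that the trial carries a false-positive risk of about 19%, or that small cells alone create one. The documents support neither: the first needs an assumed systematic gap and a mean fall of 20%, and the second is contradicted by Step 5.

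Second, the 'and' may be loose wording. If the rule were reconciled to 'or', the thresholds above 75 would disappear. That is true, but Step 3 shows that dependence on the start would remain below 75.

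Third, the plan already covers part of this. Heart rate is recorded before the procedure, group comparisons of the measurements are planned, and anxiety is measured. These would show an imbalance in starting rate, but nothing links it to the reading of the TCR comparison. Further adjustment could sit in an analysis plan not shown; the outcome definition, however, is fixed here.

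Fourth, relative fall alone is not neutral. It looks unbiased in Step 4 only because falls were assumed unrelated to start. A raised, anxious rate that merely settles could reach 20% with no reflex, and the below-60 limb guards against that. A reader might infer that every uncounted fall is a missed reflex; the documents do not show this. This objection limits the relative-fall score to a sensitivity analysis.

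**Conclusion.** The point holds in a limited form. Under the rule as written, the required fall rises with the starting rate above 75, and this follows exactly from the protocol's wording. TCR prevalence can therefore differ between arms through starting rate alone, and some falls of 20% or more are not counted. The design offers no stated protection and the planned comparison makes no allowance.

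Whether it will mislead in this trial is not known. On assumed starts of 78 v 88, the false-positive rate ranges from under 2% (mean fall 10%, SD 8%) to 23–24% (mean fall 25%, SD 10%). It reaches about 29% if the SD at that mean fall is 8%, so the upper figure is not a ceiling. These figures need a systematic gap, which the documents do not establish. The conclusion also rests on reading 'and' literally and on taking the pre-procedure rate as the reference, which the rule itself does not name.

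**What to change.** Reconcile the 'and' rule (Materials and Methods Section, Scope of the research, Evaluation of results) with the 'or' definition (Introduction-Purpose Section, Purpose of the research), and use one wording throughout. Which wording is right is for the investigators. Keep the reconciled rule for the headline count.

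Add, before data are seen: *TCR is also reported by arm on the relative heart-rate fall alone (20% or more from the pre-procedure value), with the below-60 limb reported separately, and starting heart rate is tabulated by arm. If the arm difference in the headline count is not similar in direction and size under the relative-fall score, it is reported as possibly due to starting rate.*

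The cost is a short paragraph and an extra row per comparison, from heart rates already recorded. The downside is a second TCR figure to explain, which may include falls that are only an anxious rate settling.

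### The only stated power (90%, n=20, effect size 0.42) names no test, metric or endpoint and is not shown to apply to the planned comparisons of four arms of 10

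*Protocol*

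**What the plan says.** The paragraph appears twice in the Protocol, under 'Sample Selection and the statistical method to be used' and in the 'Statistical Analysis' row of the application form. It says "the power and sample level of the study were calculated with reference to the study of" a cited trial of 20 patients. By its title in the reference list, that trial concerned a different operation, bilateral sagittal split ramus osteotomy.

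The paragraph continues "n=20 patients planned to be included in the study planned the study with 90% power", adds as its yardstick that "values of 0.70 and above are considered valid and 0.80 is considered to be quite sufficient", and concludes "it was determined that the effect size level was 0.42. The study is planned to be conducted on a total of 40 patients". The 40 are then split into four groups of 10. No step leads from 20 to 40, and no power is attached to the 40.

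The arms combine nerve proximity with anaesthesia technique: "2 groups according to the anesthesia technique to be applied (Gow-Gates Block - Inferior alveolar block). Total research arm is 4" (Materials and Methods). On the outcome, "The prevalence of TKR will be evaluated in 4 separate groups according to whether Gow-Gates anaesthesia or nervus alveolaris inferior anaesthesia is applied". For group differences in the measurements, "independent Mann Wihtney U test and Kruskall Wallis test analyses are considered"; for change over the recorded stages, "Paired Wilcoxon test and Friedman test analysis can be applied in the evaluations of repeated measurements". Chi-square is planned for proportions, the significance level is 0.05, and the power software is named (G*Power 3.1.7) without a test family.

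**The concern.** A power figure has meaning only for a stated test, effect-size metric, endpoint and sample size. Here only the last is given, and it is the cited trial's 20, not the planned 40. The allocation to four arms follows almost at once, so a reader can easily carry the 90% over to the arm comparisons and expect one missed effect in ten.

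If 0.42 is one of the usual between-group metrics, the miss rate under conventional assumptions is higher. A non-significant difference between techniques or proximity groups could then be reported as adequately powered evidence of no difference. The protocol does not call these comparisons confirmatory, which limits the harm but does not remove it.

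**Working it through.** **Inputs from the Protocol.** Effect size 0.42, power 90% and n=20; planned N=40 as 4 x 10, hence 20 v 20 when pooled by technique or by proximity; alpha 0.05.

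**Assumptions, because the Protocol is silent.** Two-sided tests. The metric is tried as f, w and d. Rank tests are simulated with normal data (20,000 runs). Chi-square power is large-sample unless marked exact.

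**Step 1: can 90% at n=20 be reproduced?** For f or w the noncentrality is λ = 0.42² x N = 0.1764 x 20 = 3.53.
- f, four groups: ANOVA (noncentral F) 26%; Kruskal-Wallis 20-21%.
- f, two groups (d = 2f = 0.84), 10 v 10: t-test 43%; Mann-Whitney 42%.
- w, chi-square: 32% (df 3); 47% (df 1).
- d = 0.42, 10 v 10: t-test 14%; Mann-Whitney 15%.
- Single paired contrast, standardised difference 0.42: t-test 43%; Wilcoxon 41%.
- Friedman over four stages, f = 0.42: 76%, 90% and 97% at assumed within-patient correlations of 0, 0.3 and 0.5.

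None of these between-group readings gives 90%. A planned within-patient test can, with a correlation that the Protocol does not state. The 90% can therefore be neither confirmed nor refuted.

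**Step 2: power of the arm comparisons at N=40.** λ = 0.1764 x 40 = 7.06. For two groups of 20 the t noncentrality is d x √(20/2): 0.84 x 3.162 = 2.66 on the f reading and 0.42 x 3.162 = 1.33 on the d reading.

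| 0.42 read as | Four arms of 10 | 20 v 20 |
|---|---|---|
| f | Kruskal-Wallis about 50% (ANOVA 54%) | Mann-Whitney about 71% (t-test 74%) |
| w | chi-square df 3, 59% | chi-square df 1, 76% |
| d | not applicable | Mann-Whitney about 24% (t-test 25%) |

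The critical values are F(3,36) = 2.87, chi-square 7.81 (df 3) and 3.84 (df 1), and t(38) = 2.02.

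**Step 3: how far do the assumptions move these figures?**
- Exact Pearson 20 v 20, w = 0.42, at overall incidence 50, 40, 30, 20 and 15%: 76, 78, 80, 84 and 89%. At 10% incidence, w = 0.42 is not attainable.
- Exact four-arm Pearson, w = 0.42, incidence 6-50%, five patterns: 40-68%.
- Rank tests with f = 0.42 in SD units and non-normal data: Mann-Whitney 20 v 20 about 83% (Laplace), 90% (exponential) and 92% (t, 3 df). Four-arm Kruskal-Wallis is 63-65% for Laplace and roughly 76-79% for the other two.
- 0.42 as f-squared (f = √0.42 = 0.648): Kruskal-Wallis 89%, Mann-Whitney 97%. As eta-squared (f = √(0.42/0.58) = 0.851): 99% and over 99%. The text supports neither metric.

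**Step 4: miss rates (100% minus power).** Four arms: about 50% (f, normal) or 41% (w; exact 32-60%). For 20 v 20: about 29% (f, normal), 24% (w; exact 11-24%) or 76% (d).

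**The case against.** The strongest reply is that the Protocol never claims 90% for the four arms. Its sentence ties 90% to n=20 and to the cited trial, and the 40 patients come later with no power attached. The figure may also be right for something else. Friedman over four stages gives about 90% at n=20 with a correlation of 0.3, and a group-by-time interaction with four groups, three times and correlation 0.5 gives 90.1%, although the latter test is not planned. The stated purpose is the frequency of the reflex, and no comparison is named primary. All of this stands, and it means that the 90% is not shown to be an arithmetic error. It does not supply power for the arm comparisons, and a paragraph offered as this study's own power calculation does not say that they have none.

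A second reply concerns the stronger inference that no planned between-arm test could reach 90% if 0.42 is f, w or d. The documents do not support that. They state no distribution, and on the f reading Mann-Whitney 20 v 20 reaches about 90-92% under exponential or t (3 df) data. On the w reading the exact 20 v 20 test reaches 89% at 15% incidence. The lower figures hold only under the assumptions listed with them.

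**Conclusion.** The point holds as a gap in the stated power. The Protocol offers 90% as the study's power calculation without test, metric or endpoint, and gives none for the design it adopts.

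Under conventional assumptions, 0.42 read as f, w or d does not give 90% for the planned between-arm tests at N=20 or N=40. At N=40 the range is about 24% (d, 20 v 20) to 76% (w, 20 v 20, large-sample; 76-89% exact). On f or w the four-arm tests, at about 50% and 59%, also fall below the Protocol's own 0.70, while the 20 v 20 contrasts do not.

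These sizes depend on the metric, the distribution and the incidence, none of which is stated. A reader might infer that 90% is miscalculated, or that the Protocol asserts 90% for the four arms. The text establishes neither. The point should be corrected, at little cost.

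**What to change.** Keep 40 patients and change the paragraph in both places:

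1. From the saved G*Power input, name the test, effect-size metric and endpoint behind 90% and 0.42.
2. State that the 90% applies only to that test at n=20, and not to the four-arm design.
3. Recompute and state power at N=40 for the planned four-arm and 20 v 20 tests, with the distribution or incidence assumed. The percentages above are illustrative and should not be copied in.
4. If 0.42 is a within-patient effect, say that no arm comparison was powered.
5. Where the restated power is below the Protocol's own 0.70, add that a non-significant arm comparison is not evidence of no difference.

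The cost is one look-up, a short calculation and the rewording of one paragraph that occurs twice. Patients, arms, endpoints and tests stay as they are. The stated power may become less favourable.

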Statistical Analysis	
Since the study population was not known, the power and sample level of the study were calculated with reference to the study of Bohluli (2011). Bohluli (2011) studied with n=20 patients in his study. According to the study of Bohluli (2011), it is seen that n=20 patients planned to be included in the study planned the study with 90% power (in studies, values of 0.70 and above are considered valid and 0.80 is considered to be quite sufficient). In the study, it was determined that the effect size level was 0.42. The study is planned to be conducted on a total of 40 patients. The groups were determined equally as Group 1 (IAS / less than 1 mm distance) n=10, Group 2 (IAS / more than 1 mm distance) n=10, Group 3 (IAS / less than 1 mm distance) n=10 and Group 4 (IAS / more than 1 mm distance) n=10.
 
Regarding the analysis of the data; descriptive statistics will be presented with mean-d.deviation, median-IQR, frequency and percentage values. In order to examine whether the measurements in the study are different according to the characteristics of the study groups, independent Mann Wihtney U test and Kruskall Wallis test analyses are considered. Paired Wilcoxon test and Friedman test analysis can be applied in the evaluations of repeated measurements. In determining the times that are significant as a result of Friedman test, it is considered to be determined by All-pairwise method. Spearman correlation analysis will be applied to examine the relationships between the measurement values of the groups. Chi-square analysis will be performed for the proportional evaluations of the groups. In the study, p values less than 0.05 are considered significant. The analyses will be analysed with

	SPSS 25.0. Power level and effect size calculations calculated in the study were determined with G*Power Version 3.1.7.	
Coordinator	Coordinating centre	Kütahya Health Sciences University Faculty of Dentistry Department of Oral, Dental and Maxillofacial Surgery Kütahya Health Sciences University Faculty of Dentistry Department of Oral, Dental and Maxillofacial Surgery
	Coordinator (principal investigator in single-centre studies)	[name]
	Contact	[name] [contact]
Administrative Responsible (if applicable)	Name and surname	-
	Place of assignment	-
	Contact	-

Research centres

	Research centres	Principal Investigator (Area of Expertise) (Telephone)

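### The Friedman all-pairwise follow-up discards the size of each patient's change between stages; Holm-adjusted paired Wilcoxon tests, already among the listed methods, would locate the stage better with all 40 patients

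*Protocol*

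**What the plan says.** Under Materials and Methods the protocol sets the measurement times: "The records will be taken in 4 stages: before starting the surgical procedure, during the application of local anaesthesia, during the incision", and finally during elevation of the crown and root. Heart rate, systolic and diastolic pressure and oxygen saturation are recorded, and all four are listed in the Outcome/Endpoint row of the application form.

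The section on sample selection and statistical method, repeated in the Statistical Analysis row of the application form, says of these data: "Paired Wilcoxon test and Friedman test analysis can be applied in the evaluations of repeated measurements". It then says how the differing stages are found: "In determining the times that are significant as a result of Friedman test, it is considered to be determined by All-pairwise method". The significance rule is "In the study, p values less than 0.05 are considered significant" and the software is given by "The analyses will be analysed with SPSS 25.0". No adjustment for the number of pairs is named, and no contrasts are named for the Wilcoxon test.

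The introduction describes the reflex as "a decrease in heart rate and mean arterial blood pressure by more than 20% from baseline", or a heart rate under 60, so the change of interest is a fall from a reference reading.

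**The concern.** Four stages give six pairs, and three of them do not involve the pre-procedure reading. After a Friedman test, the all-pairwise method replaces each patient's four readings by ranks 1 to 4 and compares the mean ranks of two stages. A fall of 3 beats and a fall of 30 beats can receive the same rank. The result for one pair also depends on where the other two stages fall in the ranking. A paired Wilcoxon test ranks the patients' changes by size and uses only the two stages concerned.

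Each arm has only 10 patients, but the within-patient stage comparison can use all 40. If the follow-up test is weak, a real fall at one stage may go unlocated. If it is read without adjustment, a stage may be named that does not differ.

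**Working it through.** **No figure to reproduce.** The protocol gives no power, SD or correlation for stage comparisons. Its one effect size ("In the study, it was determined that the effect size level was 0.42") has no stated type, outcome or test, so it cannot be taken as a stage-to-stage effect. A value of 0.42 appears below only as one point in a range.

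**Inputs from the protocol:** k = 4 stages, n = 40 in total, 10 per arm, significance level 0.05 (two-sided assumed).

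**Assumptions:** normal data; equal within-patient correlation of 0.6 wherever a correlation is quoted; a fall at elevation only, in SD of the paired difference; all-pairwise output taken as a z test on mean ranks with a Bonferroni factor of 6.

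**The rank criterion.** Pairs: 4 × 3 / 2 = 6. Standard error of a mean-rank difference: √(k(k+1)/(6n)). At n=40 this is √(20/240) = 0.289. Critical z at 0.05/6, two-sided: 2.638. Two stages must therefore differ by 2.638 × 0.289 = 0.76 mean ranks. At n=10 the standard error is √(20/60) = 0.577 and the threshold is 2.638 × 0.577 = 1.52.

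**Simulated power for elevation against the pre-procedure reading** (8,000 to 40,000 runs per row; the Wilcoxon column uses 0.05/3 per contrast):

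| n | Fall (SD) | Friedman, then all-pairwise with factor 6 | Three Wilcoxon contrasts | Gap (points) |
|---|---|---|---|---|
| 40 | 0.30 | 15.0% | 27.5% | 12.6 |
| 40 | 0.42 | 34.1% | 54.5% | 20.4 |
| 40 | 0.50 | 50.8% | 72.4% | 21.7 |
| 40 | 0.60 | 70.6% | 88.2% | 17.7 |
| 40 | 0.80 | 94.2% | 99.1% | 4.9 |
| 10 | 0.42 | 4.6% | 8.7% | 4.1 |
| 10 | 0.50 | 6.8% | 12.5% | 5.7 |

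Gaps were taken before rounding. A separate run with Holm adjustment and correlation 0.6 gave 35% against 56% at 0.42 SD and 51% against 71% at 0.5 SD. Across the two sets the gap peaks at about 21 points.

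**Where the loss arises** (n=40, 0.42 SD). The rank test rises from 34.1% to 45.0% when 0.05/3 replaces a significant Friedman test plus 0.05/6: 10.9 points. Replacing joint ranks by Wilcoxon takes it from 45.0% to 54.5%: 9.5 points. The sum is 20.4.

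**Each pair read at 0.05, with no factor.** At n=40 and 0.42 SD, power is 54% against 56% for the three Holm contrasts. About 10% of runs then flag at least one of the three pairs that do not differ.

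**A fall in a minority.** If 30% of patients fall by 3 SD (n=40), power is 29% with factor 6 and 66% with three Holm contrasts, a gap of 37 points. Without the factor, the rank method still reaches only 44%. If only 10% of patients fall, both methods fail (2% against 7%).

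**Keeping all six pairs, by Holm-adjusted Wilcoxon** (n=40, against all-pairwise with factor 6): 65% against 51% at 0.5 SD, and 58% against 29% for the 30% subset. If the reading rises by 0.6 SD at anaesthesia and incision and then returns at elevation, the elevation-incision pair is found in 87% of runs against 72%. Family-wise error stayed at or below 5%. Within a 10-patient arm six pairs bring no gain: at 0.42 SD, Wilcoxon at 0.05/6 has 4.4% against 4.6%.

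**The case against.** Friedman with an all-pairwise follow-up is a standard procedure and, when adjusted, controls error. The wording is tentative, the paired Wilcoxon test is already permitted, and naming contrasts and adjustments is commonly left to an analysis plan that is not at hand. All of this stands: the missing adjustment is not the point, and the procedure is not invalid. What remains is that the one sentence saying how differing stages are located names the weaker method.

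It can also be said that three baseline contrasts are too few. The protocol records sudden changes with the step at which they occur and gives both a fall and a rise as examples. A drop from incision to elevation would never be tested against the pre-procedure reading. This is sound, and it is why the fix offers a six-pair option.

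Three stronger readings are tempting and are not supported:

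- A reader might infer that the plan as written splits alpha over six pairs and costs about 20 points of power. The protocol states no such split. The factor of 6 is an assumption about software output, and the loss varies widely with effect size and sample size.
- A reader might infer that the reflex itself would be missed. It is counted patient by patient on a heart-rate threshold, and proportions are compared by chi-square. The Friedman follow-up does not enter.
- A reader might take 0.42 as the expected stage effect. The protocol never defines it so.

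**Conclusion.** The point holds in conditional form, as an improvement worth making rather than an error that invalidates the plan. With a factor of 6 and n=40, the stated method gives up about 13 to 21 points for falls of 0.3 to 0.6 SD of the difference, about 5 at 0.8 SD and over 35 if 30% of patients fall by 3 SD. Within one arm it gives up about 4 to 6 points at 0.42 to 0.5 SD, where power is low either way. With no factor, the uniform-shift loss nearly vanishes and about 10% of runs give a false finding among the null pairs. The loss from ranking away a large fall in a minority persists under both readings (44% unadjusted against 66%). The figures rest on normal data, assumed correlations and a fall at one stage only, none of which the protocol supplies.

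**What to change.** In the section on sample selection and statistical method, and in the Statistical Analysis row of the application form, replace the all-pairwise sentence. Keep the Friedman test as the overall test and locate stages by paired Wilcoxon signed-rank tests with Holm adjustment within each parameter. Choose one form before data are seen:

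- **All six pairs.** No contrast is lost. Power is about 65% against 51% at n=40 and 0.5 SD, with no gain inside a 10-patient arm.
- **Three contrasts against one stated reference stage.** Power is about 71% in the same case. The other pairs become descriptive, for example elevation against incision when the pre-procedure reading is the reference.

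The cost is one sentence in two places. It needs no extra patients or measurements and uses a test the plan already lists.
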